## **Study protocol for upload to ClinicalTrials.gov**

### **Standard PMCF study WSA @ HzO 2024**

**NCT06700512**

**Date of study protocol D00325215: 2024-06-12**

## **1. General**

### **1.1 Introduction**

The goal of this study is to investigate speech intelligibility and the perception of sound with a CE-marked test hearing aid (HA) in the universal program and compare the results to results obtained with the participants' own hearing aids (speech test and questionnaires) and without hearing aids (speech tests).

This study goes under the existing PMCF umbrella approval of the Hörzentrum Oldenburg gGmbH at the medical ethics committee (Oldenburg University, Votum 2022-033). For this purpose, the subjects will listen to the HA in different acoustic scenes in real-life situations, undergo laboratory speech tests in quiet and noise, and answer questionnaires.

### **1.4 Overall synopsis of the clinical investigation**

This study will investigate speech understanding, spatial reception and satisfaction with a current hearing aid of WSA as part of the PMCF Process.

The main objective of the study is to investigate if speech understanding with the WSA Hearing Aid (HA) is better than without a hearing aid and not inferior to speech understanding with the participants' own hearing aids.

The study uses a direct approach where n = 20 adult test subjects, all being experienced hearing-aid users with mild-to-moderate sensorineural hearing loss, will be fitted with test hearing aids.

The subjects will complete a test battery in the lab and an assessment in real life with the test hearing aids and their own hearing aids. The study protocol includes two visits to the lab (of duration up to two hours) and a home trial with a duration of 10-14 days. Objective speech tests performed in the lab provide measures of speech intelligibility in quiet and in noise. Subjective self-assessment performed in real-life are done by use of questionnaires where self-perceived performance of the test hearing aid and the subjects' own hearing aid is rated within the main domains of speech intelligibility, listening effort and sound quality. In addition in-situ measurements will be performed to assess the quality of WSAUD fitting to a clinical target (NAL NL2). All these measurements are described in the PMCF

umbrella approval of the Hörzentrum Oldenburg gGmbH at the medical ethics committee (Oldenburg University, Votum 2022-033). Statistical analysis of both speech-test outcomes and self-assessment ratings will be done to test the overall main hypothesis that the test hearing aid offers improved speech understanding over the unaided condition and non-inferior speech understanding and performance ratings compared to the subjects' own hearing aids.

## **2. Identification and description of the investigational device**

The study will be conducted with **CE-marked Signia Pure C&G 7IX** hearing aids with M- Receivers, together with the compatible CE-marked Pure Portable Charger. The hearing aids will have one or more programs: the universal program is programmed by default and will be used for all speech tests. More programs can be added for the home-trial upon request of the subject as per standard-of-care fitting.

### **2.2 Model/Type**

Investigational devices PURE C&G 7IX M are rechargeable behind-the-ear hearing aids with receiver in the canal (RIC). For all subjects a M receiver will be used, length will be selected according to individual anatomy. Depending on hearing loss, devices will be fitted with open, semi-open or power (closed) earwear. For charging the devices the portable charger RIC is provided. User guide and data are available on-line. The user guide is also available as printed version for all subjects.

As benchmark the subjects' own devices will be used with the fitting that has been provided by the hearing care professional of the subject.

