## **4.2 Hypotheses**

### **4.2.1 Primary objectives**

The **primary objectives 1 and 2** will be addressed by measuring a speech reception threshold (SRT) for each hearing aid, using an adaptive speech-in-noise test, OLSA. The SRT corresponds to the signal-to-noise ratio (SNR) where 80% of the words presented are correctly repeated by the test subject. Thus, a lower SRT value indicates better performance.

The difference between the study HAs and the subjects' own HAs or no HAs will be assessed as the mean SRT difference. The expectation is that the study HAs give an advantage over not wearing HAs so the first hypothesis is:

**$H_0$  (Objective 1)** SRT(study HA) is not significantly different from SRT without HAs

**$H_1$ (Objective 1)** SRT(study HA) is significantly better than SRT without HAs

A mean difference in SRT of 1 dB measured with the Oldenburg sentence test (Wagener et al, 1999a-c), can be assumed as a typical difference in speech intelligibility to show a clinically meaningful improvement (Kollmeier et al, 2011).

In addition, the expectation is that the study HAs are not inferior to the subjects' own HAs:

**$H_0$  (Objective 2)** SRT(study HA) is significantly worse than SRT(own HAs).

**$H_1$ (Objective 2)** There is no difference between SRT(study HA) and SRT(own HAs)

A significant difference means that the study HAs are inferior to own HAs, otherwise they are non-inferior. .

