#### **Inclusion criteria:**

- The allowed audiometric range for HIL is shown below:

- They should be experienced hearing aid users
- Air-Bone-Gap should be less or equal to 20 dB HL.
- Sensorineural HV, mild-to-moderate
- HV corresponding to the fitting range of the HA
- Healthy (outer) ear
- Older than 18 years
- German is mother tongue
- Able to understand the instructions
- Willing to participate in laboratory tests and to wear the HAs at home for 2 weeks
- Informed consent

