## **7.2 Statistical analysis**

**Objectives 1 and 2** (Speech in Noise OLSA): The SRT data will be analyzed using a one-tailed paired t-test.

**Objectives 3 and 4** (Speech in Quiet Freiburger): Similarly to the OLSA Test the % correct data will be analyzed using a one-tailed paired t-test.

**Objective 5** (NAL-NL2 Targets): No statistical analysis will be performed, only descriptive statistics will be used.

**Objectives 6-7** (Questionnaires – SSQ17, IOI-HA)

Subjective rating data from real-life questionnaires will be analyzed using one-tailed paired t-tests, comparing ratings of study HA and own HA with a significance level of 0.05 to determine significance.

In addition, descriptive statistics of the SSQ 17 scores and IOI-HA scores will be reported by Hearing Aid (study or own) for each subscale and put into perspective of published data (von Gahlenz et al, 2018; Cox et al, 2013).

**Objective 8** (Questionnaire – Satisfaction)

One-sided test of proportions will be done to analyze whether the proportion of satisfied hearing aid users is significantly lower with study hearing aids than reported in the literature (MarkeTrak 10, EuroTrak). A significant effect indicates that the study hearing aids are inferior, otherwise they are non-inferior.

In addition, subjective rating data from satisfaction questionnaire will be analyzed using one-tailed paired t-tests, comparing ratings of study HA and own HA with a significance level of 0.05.

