### **9.4 Randomization and blinding coding**

The study design does not allow for the study to be blinded. REM Measurements will only be done with the study HAs and during Home-Trial, subjects are well aware of which HA they are wearing. For the speech tests the order of study HA, own HA and unaided will be randomized.

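### Objectives 2 and 4 rest on own hearing aids taken as found, and the own-versus-unaided contrast measured in the same session is not analysed, so a non-inferior result does not show whether the benchmark worked

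*Combined protocol and SAP*

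**What the plan says.** The comparator for Objectives 2 and 4 is the subject's own aid as it stands. Under section 2.2 the subjects' "own devices will be used with the fitting that has been provided by the hearing care professional". The only entry requirement in section 6.1 that bears on the own aid is "They should be experienced hearing aid users"; its age, condition, current fit and benefit are not mentioned. Section 9.4 adds that "REM Measurements will only be done with the study HAs".

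All three conditions are tested at the second lab visit (section 6.3), and section 9.4 says "For the speech tests the order of study HA, own HA and unaided will be randomized".

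The planned contrasts are fewer than the measured ones. Section 4.2.1 says "The difference between the study HAs and the subjects' own HAs or no HAs will be assessed as the mean SRT difference", and section 4.2.2 sets up the same two comparisons for the Freiburger score. Section 7.2 says "The SRT data will be analyzed using a one-tailed paired t-test" for Objectives 1 and 2, and "the % correct data will be analyzed using a one-tailed paired t-test" for Objectives 3 and 4. No objective, hypothesis or analysis compares own HA with unaided.

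The decision rule for Objective 2 is "A significant difference means that the study HAs are inferior to own HAs, otherwise they are non-inferior", and section 4.2.2 repeats it for Objective 4. Neither rule refers to the result of Objective 1 or 3. The synopsis (section 1.4), however, states one overall main hypothesis that joins improvement over unaided with non-inferiority to own aids.

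**The concern.** Non-inferiority to an active control is informative about effectiveness only if the control was effective in the same setting. Here the control is heterogeneous and unverified. The one contrast that would show whether it worked, own HA against unaided in the same subjects and session, is collected and left unused. A reader of a non-inferior result cannot tell whether the study HA kept up with working aids or with aids that gave no measurable advantage in this set-up. Because the rules for Objectives 2 and 4 stand alone, the plan also does not say how to report non-inferiority when Objective 1 or 3 fails. What is at stake is the meaning of one of the two primary results and of its counterpart in quiet.

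**Working it through.** **Inputs.** From section 7.1: effect 1 dB, SD 1.3 dB, correlation 0.8, dz 0.77, alpha 0.05, n = 16, recruited N = 20, power 0.9 at N = 20. From section 7.2: one-tailed paired t-tests. Assumed here: the same SD and correlation for all three pairings of conditions, normal data, and a one-sided 0.05 test of own HA against unaided.

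**1. The plan's own figure.** Exact paired t-test power with dz = 0.77 and two-sided alpha 0.05 gives 0.821 at n = 16 and 0.904 at n = 20. Both stated figures reproduce.

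**2. SD of the paired difference.** SD_d = SD × √(2(1 − r)). The stated dz implies 1/0.77 ≈ 1.3 dB, which corresponds to r = 0.5. The stated r = 0.8 gives 1.3 × √0.4 = 0.822 dB. That mismatch is a separate matter; 1.3 dB is used below, with 0.822 dB as the alternative.

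**3. The Objective 2 rule alone.** Non-inferiority is declared unless t = (mean study SRT − mean own SRT)/(SD_d/√n) exceeds the one-sided 5% critical value. For a true deficit δ, the probability of declaring it is the noncentral t distribution function at that value, with n − 1 degrees of freedom and noncentrality δ√n/SD_d.

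| True deficit of study HA against own HA | SD_d 1.3, n = 20 | SD_d 1.3, n = 16 | SD_d 0.822, n = 20 | SD_d 0.822, n = 16 |
|---|---|---|---|---|
| 0 dB | 0.95 | 0.95 | 0.95 | 0.95 |
| 0.25 dB | 0.79 | 0.82 | 0.63 | 0.69 |
| 0.5 dB | 0.50 | 0.57 | 0.16 | 0.25 |

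If own HA equals unaided, these are also the probabilities of declaring a study HA non-inferior when it is no better than, or worse than, no aid.

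**4. What the result reveals about the benchmark.** In simulation (SD_d 1.3, n = 20), non-inferiority is declared with probability 0.951 when both aids give 0 dB, 0.951 when both give 0.5 dB and 0.950 when both give 1 dB. The result does not distinguish these cases.

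**5. The joint claim.** With neither aid helping (n = 20), non-inferiority is declared while Objective 1 fails in 0.903 of trials. Both parts succeed in 0.951 − 0.903 = 0.048.

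**6. Would a margin cure it?** With a 1 dB margin and both aids giving no benefit, the noncentrality is √20/1.3 = 3.44 at n = 20 and √16/1.3 = 3.08 at n = 16. Non-inferiority is then shown with probability 0.952 and 0.901. A margin alone does not show that the benchmark works.

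**7. Effect of the proposed reporting rule** (SD_d 1.3). The result stays interpretable if non-inferiority is declared and at least one aided condition beats unaided. The probability is P(declared and study HA beats unaided) + P(declared and own HA beats unaided) − P(declared and both beat unaided).
- Neither aid helps, n = 20: 0.049 + 0.038 − about 0.01 = about 0.08, against 0.95 without the rule.
- Both give 1 dB, n = 20: 0.912 + 0.903 − about 0.88 = about 0.94.
- Both give 1 dB, n = 16: 0.867 + 0.853 − about 0.80 = about 0.92.

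When both give 1 dB, own HA itself also beats unaided in 0.903 (n = 20) or 0.853 (n = 16). In the remaining 0.94 − 0.90 = 0.04 or 0.92 − 0.85 = 0.07, the result carries the more cautious wording set out in the fix.

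**8. Objective 4.** The same rule gives 0.95 at zero true difference. The documents give no SD for the Freiburger score, so nothing further is computed.

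**The case against.** Several points on the other side stand.

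- Own aids as worn are a legitimate real-world benchmark. For that question, unselected age and fitting belong to what is being compared.
- Section 1.4 joins superiority over unaided with non-inferiority to own aids, so an ineffective study HA would seldom support the main hypothesis (step 5). This is not a formal gate, but it does state the claim.
- The 95% is chiefly a property of a rule with no margin at zero true difference, and it would be the same for two excellent aids. It measures how little the result says about the benchmark, not a separate harm from unverified aids.
- If the study HA beats unaided and own HAs do not, calling the study HA non-inferior to own HAs is true. A strict requirement that own HAs beat unaided would label Objective 2 uninformative in about 95% of trials in which the study HA gives 1 dB and own HAs give none. That is too harsh.

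A reader might also draw stronger inferences that the documents do not support:

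- *Real-ear measurement verifies the study HA but not the own HA.* Under section 6.2 the measurement is made on a NAL-NL2 fit, after which the study HAs are refitted with the proprietary formula. It serves Objective 5 and does not verify the study HA as used in the speech tests.
- *Subjects who own the test model dilute the comparison.* Nothing indicates that there are any, and their own aids would keep a different fitting, so a zero difference does not follow.
- *The result will be presented as equivalence to current hearing-aid care.* The plan claims only against the subjects' own aids.

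Finally, some sections (1.2, 1.3 and 2.1) and the umbrella approval were not available for this review, and anamnesis at the first visit may already record own-aid details. The design, workflow and analysis sections contain no check.

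**Conclusion.** The point holds as a gap in interpretation. Own HAs are used as found, the contrast that would show whether they worked is measured but not analysed, and the rules for Objectives 2 and 4 do not depend on any aided benefit. If neither aid helps, Objective 2 alone yields non-inferiority in about 95% of trials, about 90% with Objective 1 failing. It does not follow that the trial could establish efficacy for a useless device: the claim against unaided is tested directly and would succeed falsely in at most about 5%. Nor does it follow that own aids are an invalid comparator.

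The zero-difference figure holds for any SD. The figures for the effect of the fix assume SD_d 1.3 dB for every pairing and apply to OLSA only.

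**What to change.** In section 7.2, beside Objectives 2 and 4, add the paired own-HA minus unaided mean difference with its confidence interval for OLSA SRT (negative favours the aid) and Freiburger percent correct (positive favours the aid). State the test used to judge whether an aided condition beats unaided, and then, for each speech test:

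- If neither aided condition beats unaided, the non-inferiority result is reported as uninterpretable.
- If the study HA beats unaided but own HAs do not, it is reported as a comparison with own aids as worn that showed no measurable benefit, not as non-inferiority to effective aids.
- If own HAs beat unaided, the result is reported as planned, beside the result of Objective 1 or 3.

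Recording the make and model of the own aids is optional. No exclusion of test-model owners and no strict own-beats-unaided gate is needed.

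The cost is one extra paired comparison per speech test, with no added subjects or measurements. The downside is an occasionally withheld claim: when both aids give 1 dB, the probability of an interpretable non-inferiority result falls from 0.95 to about 0.94 (n = 20) or 0.92 (n = 16). For Freiburger this loss is unknown without an SD. The missing margin needs its own correction; this change does not replace it.

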### **2.3 Traceability**

Study HA are traced by serial numbers. All study HAs will be shipped to the study partner prior to study start and will be returned to the sponsor when the study is completed.

## **3. Justification for the design of the clinical investigation**

Listening to speech in background noise is a challenging task for people with hearing loss. The loss of audibility and the reduction of temporal and spectral resolution, which are the typical consequences of a sensorineural hearing loss, will result in degraded ability to understand speech, in particular in background noise. For people with hearing loss not using hearing aids, "trying to follow conversations in noise" is the situation among several daily-life situations where the lowest listening satisfaction was observed in the MarkeTrak 10 survey (Picou, 2020). Even though use of hearing aids improves the level of satisfaction, the level of listening satisfaction is still lower for noisy conversations than in most other situations among people with hearing loss who use hearing aids (Picou, 2020).

In the development of hearing aids, use of noise reduction and directionality has for decades been used to improve speech-in-noise performance by offering signal-to-noise improvements and improved comfort in noise.

When fitting hearing aids, the compensation of hearing loss is accomplished by fitting formulas that translate the audiogram data into a recommendation of gain for different input levels. Fitting formulas aim to restore audibility while maintaining comfortable loudness (Byrne and Dillon, 1986; Keidser et al 2012; Scollie et al 2005) to ensure benefit for the user.

Ensuring hearing loss compensation by fitting to prescriptive target levels such as NAL NL2 (Keidser et al 2011) has been shown to lead to improved speech quality and intelligibility while maintaining listening comfort (Bentler and Ricketts, 2016; Byrne and Cotton, 1988; Johnson et al, 2016; Moore et al, 2001). Thus clinical benefit of the hearing loss compensation provided is expected if the hearing aids can provide the gain recommended by the fitting formulas (“target”). Real ear measurements using probe microphones are considered best practice as a reliable and accurate procedure to determine how well a hearing device matches a given target while in the ear of the hearing aid user.

### **3.1 Background for the used measurements in the trial**

To investigate speech intelligibility (SI) performance for speech at 65dB in a quiet listening situation, the **Freiburger monosyllabic speech test** is used which is still the gold standard for Hearing Care Professionals in Germany. For more details, see e.g., Hahlbrock (1953).

To investigate SI performance in a noisy listening situation, **Oldenburger Satztest (OLSA)** with speech from the front (0°) and 65 dB SPL noise (OLnoise) continuously played back from the back (180°), adapting to speech recognition threshold of 80% (STR80) is used. Oldenburger Satztest is a state-of-the-art test to investigate this. More details can be found here: <https://www.hz-ol.de/de/diagnostik-olsa.html> or in Wagener et al. (1999).

To investigate the satisfaction and performance in various real-life listening situation, subjects will wear test hearing aids in their daily life and answer questionnaires (**SSQ17 and IOI-HA questionnaires**, **Satisfaction questionnaire**, to give subjective ratings on absolute rating scales with respect to perceived sound quality of conversation partners, of their own voice and of surrounding sounds, speech intelligibility, localization, audible artifacts, and overall satisfaction.

To investigate the ability to reach NAL-NL2 insertion gain targets, in-situ measurements will be done with probe mics placed close to the eardrum and ISTS noise played from the front. With this it will be documented how close the insertion gain matches the postulated NAL-NL2 targets (Keidser et al 2011) after “first fit” and after “fine-tuning”.

## **4. Study Goals: Objectives and hypotheses of clinical investigation**

The overall goal of this study is to investigate speech intelligibility and satisfaction with hearing aid performance experienced by test subjects when using the test hearing aids in lab and real-life situations. For this purpose, the subjects will undergo speech tests in quiet and noise, and they will listen and rate their sound perception in real life.

### **4.1 Study objectives**

#### **Primary objectives**

Objective 1: Investigate whether speech intelligibility in noise is better with the study HAs than without, as measured by the OLSA test (German version).

Objective 2: Investigate whether speech intelligibility in noise with the study HAs is non-inferior (i.e. the same or better) compared to speech intelligibility in noise with the subjects' own HAs, as measured by the OLSA test (German version).

### **Secondary objectives**

Objective 3: Investigate whether speech intelligibility in quiet is better with the study HAs than without HAs as measured by the German Freiburger test.

Objective 4: Investigate whether speech intelligibility in quiet with the study HAs is non-inferior (i.e. the same or better) compared to speech intelligibility in quiet with the subjects' own HAs as measured by the German Freiburger test.

Objective 5: Investigate how close the study hearing aids fitted with the fitting software to NAL-NL2 Targets match the postulated targets, as measured in-situ with real-ear measurements.

Objective 6: Investigate speech perception, sound localisation, satisfaction and quality of hearing perceived in real-life with the study hearing aids compared to the subjects' own hearing aids as measured by the SSQ17 questionnaire (German version)

Objective 7: Investigate outcomes and effectiveness of hearing aid usage in real-life with the study hearing aids compared to the subjects' own hearing aids as measured by the IOI-HA questionnaire (German version)

Objective 8: Investigate satisfaction in real-life with the study hearing aids compared to the subjects' own hearing aids as measured with the Satisfaction questionnaire (WSA internal questionnaire)

## **4.2 Hypotheses**

### **4.2.1 Primary objectives**

The **primary objectives 1 and 2** will be addressed by measuring a speech reception threshold (SRT) for each hearing aid, using an adaptive speech-in-noise test, OLSA. The SRT corresponds to the signal-to-noise ratio (SNR) where 80% of the words presented are correctly repeated by the test subject. Thus, a lower SRT value indicates better performance.

The difference between the study HAs and the subjects' own HAs or no HAs will be assessed as the mean SRT difference. The expectation is that the study HAs give an advantage over not wearing HAs so the first hypothesis is:

**$H_0$  (Objective 1)** SRT(study HA) is not significantly different from SRT without HAs

**$H_1$ (Objective 1)** SRT(study HA) is significantly better than SRT without HAs

A mean difference in SRT of 1 dB measured with the Oldenburg sentence test (Wagener et al, 1999a-c), can be assumed as a typical difference in speech intelligibility to show a clinically meaningful improvement (Kollmeier et al, 2011).

In addition, the expectation is that the study HAs are not inferior to the subjects' own HAs:

**$H_0$  (Objective 2)** SRT(study HA) is significantly worse than SRT(own HAs).

**$H_1$ (Objective 2)** There is no difference between SRT(study HA) and SRT(own HAs)

A significant difference means that the study HAs are inferior to own HAs, otherwise they are non-inferior. .

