#### **4.2.2 Secondary objectives**

For the **secondary objectives 3 and 4**, Speech intelligibility (SI) in quiet will be assessed with the Freiburger monosyllabic speech test where the outcome measure is percent correctly repeated words. The hypotheses related to the third and fourth objectives are:

**H0 (Objective 3)** SI(study HA) is not significantly different from SI without HAs

**H1(Objective 3)** SI(study HA) is significantly better than SI without HAs

**H0 (Objective 4)** SI(study HA) is significantly worse than SI(own HAs).

**H1(Objective 4)** There is no difference between SI(study HA) and SI(own HAs)

A significant difference means that the study HAs are inferior to own HAs, otherwise they are non-inferior.

The **secondary objective 5** will be assessed by calculating the absolute differences between the NAL-NL2 Target curves (Keidser et al 2011) realised in the Otometrics/Natus Freefit and the measured REAR/REIG curves after First Fit and after Fine-Tuning, if applicable. The expectation is that the deviation from the target curves is  $\leq$  5dB in the frequency range 0.25-4 kHz

The **secondary objective 6** will be addressed by asking the participants to rate speech understanding, localization and quality of sound in different situations as well as listening effort after having worn the hearing aids 10-14 days in real-life on a scale from 0-10 with a shortform of the SSQ questionnaire (SSQ 17 German Version, Kiessling 2011) in different situations. Mean rating will be calculated across the participants for each HA. For each domain we will test whether the ratings are significantly worse with study HAs compared to own HAs, if they are, that indicates the study hearing aids are inferior to own HAs. Otherwise, they are non-inferior.

The **secondary objective 7** will be addressed by asking the participants to rate hearing aid outcomes after having worn the hearing aids 10-14 days in real-life on a 5-point scale with IOI-HA (Cox & Alexander 2002, German Version Cox et al 2002). Mean rating will be calculated across the participants for each HA. For each question we will test whether the ratings are significantly worse with study HAs compared to own HAs, if they are, that indicates the study hearing aids are inferior to own HAs. Otherwise, they are non-inferior.

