For the **secondary objective 8**, to evaluate satisfaction, subjects are asked to rate their satisfaction with the hearing aids regarding several aspects including sound, conversations and overall satisfaction after having worn the hearing aids 10-14 days in real-life. In Marke-Trak10 survey (Picou, 2020), respondents rated their satisfaction on a 7-point scale, where 1 indicates very dissatisfied, 4 indicates neutral, and 7 indicates very satisfied. Respondents who indicated scores of 5, 6, or 7 were considered to be satisfied and satisfaction was reported as % satisfied of the study sample. In a similar manner the percentage of satisfied subjects will be calculated for the study HAs and compared to published values of (MarkeTrak10 (Picou, 2020) and EuroTrak German (2022 ), EuroTrak France (2022), EuroTrak Spain (2023) ). For each question we will test whether the proportion of satisfied subjects is significantly lower with study HAs compared to the published values (MarkeTrak/EuroTrak), if they are, that

indicates the study hearing aids are inferior the hearing aids reported on in the MarkeTrak/EuroTrak Reports. Otherwise, they are non-inferior.

In addition, mean ratings will be calculated across the participants and will be compared for the study HAs and own HAs and for each question we will test whether the ratings are significantly worse with study HAs compared to own HAs, if they are, that indicates the study hearing aids are inferior to own HAs. Otherwise, they are non-inferior.

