## 7. Statistical design and analysis

### 7.1 Sample size estimation

The sample size is determined by considering the primary objective 1 and the related hypothesis expecting a mean difference in SRT between the study HA and no HA of at least 1 dB.

Speech intelligibility in noise is usually determined as a speech intelligibility threshold in dB SNR, so a difference between dependent mean values is analyzed. The data for these data are expected to be normally distributed, so a t-test is used to estimate the number of cases.

A mean difference in SRT of 1 dB measured with the Oldenburg sentence test (Wagener et al, 1999a-c), can be assumed as a typical difference in speech intelligibility to show a clinically meaningful improvement (Kollmeier et al, 2011).

The interindividual standard deviation in hearing-impaired test subjects for this method with the stationary noise associated with the test is 1.3 dB (Wagener & Brand, 2005). Assuming that dependent mean values for two comparative measurements show a high correlation (0.8), this results in an average effect size for the method (effect size  $dz$ ) of 0.77 and, with an  $\alpha$  value of 0.05 and a  $\beta$  value of 0.2 (power = 0.8), a number of cases of  $n = 16$ , calculated using the G\*Power (3.1.9.7) program of the University of Düsseldorf (Faul et al., 2007),

With an added 25% dropout risk this suggests that recruiting 20 subjects will be appropriate with respect to addressing the primary objectives and testing the related hypothesis.  $N = 20$  subjects will provide a statistical power of 0.9 when the other parameters are kept constant.

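### Non-inferiority to the subjects' own hearing aids (primary Objective 2; secondary Objectives 4, 6, 7 and 8) is concluded from a non-significant test, with no margin

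*Combined protocol and SAP*

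**What the plan says.** Section 4.1 makes Objective 2 one of two primary objectives. Speech intelligibility in noise with the study aids is to be "non-inferior (i.e. the same or better") relative to the subjects' own aids.

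Section 4.2.1 sets the null hypothesis as the study aid being significantly worse and the alternative as "There is no difference between SRT(study HA) and SRT(own HAs"). It then gives the decision rule: "A significant difference means that the study HAs are inferior to own HAs, otherwise they are non-inferior". Section 7.2 assigns a one-tailed paired t-test to Objectives 1 and 2 and states no significance level for them.

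The only candidate for a threshold is 1 dB. Section 4.2.1 introduces it as a "typical difference in speech intelligibility to show a clinically meaningful improvement", and 7.1 uses it for sizing: "The sample size is determined by considering the primary objective 1". It is not described as a loss that may be tolerated.

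Section 4.2.2 repeats the rule for Objective 4 (Freiburger test in quiet), for each SSQ17 domain (Objective 6) and for each IOI-HA item (Objective 7): "if they are, that indicates the study hearing aids are inferior to own HAs. Otherwise, they are non-inferior". For Objective 8 it is applied to the mean ratings and also to the share of satisfied users against survey benchmarks: "For each question we will test whether the proportion of satisfied subjects is significantly lower with study HAs compared to the published values". Section 7.2 restates it for the proportions. Four of the six secondary objectives are therefore decided in this way.

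**The concern.** A one-tailed test for worse performance has no difference (or better) as its null. It cannot reject the null that 4.2.1 writes down, and a non-significant result does not establish that the study aid is as good. Non-inferiority becomes the default outcome, lost only if the data show strongly enough that the study aid is worse.

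If the study aid is truly worse, anything that weakens the test helps the claim: more variable differences, fewer subjects, a stricter alpha. A valid non-inferiority test behaves the opposite way. One of the two primary conclusions, and most of the secondary ones, would then carry no defined false-claim rate. The sample size gives no protection, because it was derived for the comparison with no hearing aid.

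**Working it through.** **Inputs from 7.1.** SD 1.3 dB (described as an "interindividual standard deviation in hearing-impaired test subjects for this method"), correlation 0.8, dz 0.77, alpha 0.05, power 0.8, n = 16, recruited N = 20, power 0.9 at N = 20.

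**Reproducing the plan's figure.** Exact paired t-test power at dz 0.77 and two-sided 0.05 is 0.821 at n = 16 and 0.904 at n = 20, matching 7.1. One-sided 0.05 would need only n = 12 and would give 0.953 at n = 20. So 7.1 was in effect computed at 0.025 per side.

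**SD of the paired differences, study minus own.** The protocol does not give it. I use three values:
- 1.3·√(2·(1 − 0.8)) = 0.822 dB, from the stated SD and correlation (this would give dz = 1.22)
- 1.3 dB, implied by dz 0.77 = 1/1.3
- 2.0 dB, an assumption to show sensitivity

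**Pass probability under the plan's rule.** Let d be the true mean of SRT(study) − SRT(own). Lower SRT is better, so d > 0 means the study aid is worse.

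P(called non-inferior) = P(T ≤ t[1−α, n−1]), with T noncentral t and noncentrality d·√n/SD.

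Example: d = 1, n = 20, SD 1.3, α = 0.05. Noncentrality = 4.472/1.3 = 3.44, critical value 1.729, probability 0.048.

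| d (dB) | SD (dB) | n=20, α 0.05 | n=16, α 0.05 | n=20, α 0.025 | n=16, α 0.025 |
|---|---|---|---|---|---|
| 0.5 | 0.822 | 16% | 25% | 27% | 38% |
| 0.5 | 1.3 | 49.5% | 57% | 63% | 70% |
| 0.5 | 2.0 | 71% | 75% | 82% | 85% |
| 1.0 | 0.822 | 0.02% | 0.1% | 0.1% | 0.5% |
| 1.0 | 1.3 | 4.8% | 9.9% | 9.7% | 18% |
| 1.0 | 2.0 | 30% | 40% | 44% | 54% |

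Here n = 16 is the requirement in 7.1 before the dropout addition (20/1.25). At d = 0 the t-test rule passes with probability 1 − α whatever n or SD is.

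**Why the rule moves the wrong way.** Let h = t[1−α, n−1]·SD/√n. The plan's rule passes if the observed mean deficit is at most h. A margin rule passes if it is below M − h. Anything that enlarges h loosens the first and tightens the second. With M = 1 dB for illustration:

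| n, SD, α | h | plan passes up to | margin rule passes below |
|---|---|---|---|
| 20, 1.3, 0.05 | 0.503 | 0.50 dB | 0.50 dB |
| 16, 1.3, 0.05 | 0.570 | 0.57 dB | 0.43 dB |
| 20, 1.3, 0.025 | 0.608 | 0.61 dB | 0.39 dB |
| 20, 2.0, 0.05 | 0.773 | 0.77 dB | 0.23 dB |

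A result just passing the plan's rule has a one-sided upper limit of 2h. At n = 20 and α = 0.05 that is 0.64, 1.01 and 1.55 dB for the three SDs.

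**Secondary objectives.** No SD is given for Objectives 4, 6, 7 or the ratings in 8. A true worsening of half an SD of the paired differences (assumption) passes 30% of the time at n = 20 and 40% at n = 16.

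For the Objective 8 proportions the benchmarks are not in the protocol. I assume 70% to 90%, a true rate 20 points lower, and one-sided 0.05. An exact binomial test passes 24–42% (n = 20) and 45–60% (n = 16); a z-test passes 24–41% and 25–40%. Section 7.2 does not say which is meant.

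**The case against.** On the plan's own inputs, exposure to a full 1 dB deficit is small. Only 0.822 and 1.3 dB trace to 7.1, and at n = 20 and one-sided 0.05 they give 0.02% and 4.8%. The second is almost what a proper 1 dB-margin test gives (5.0% at a 1 dB deficit; at no deficit, 95.0% against 95.2%). The 30% to 54% figures need an SD of 2.0 dB that the documents do not support. All of this is right, and the size should be read accordingly.

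It does not rescue the rule. The agreement arises because h happens to be close to half of 1 dB at that n, SD and alpha, and it is lost when any of them changes. The protocol never adopts 1 dB as a tolerable loss. At the same n, SD and alpha, half of all trials with a true 0.5 dB deficit would be declared non-inferior, with nothing in the protocol to say whether such a loss is acceptable.

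Section 4.1 could be read literally as a margin of zero. A non-significant result does not demonstrate that either. Under that reading, labelling a small true deficit inferior is not an error, so I do not count that direction against the plan.

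Section 12 restricts publication to descriptive statistics, but it also says the data are mainly for the PMCF report, and it leaves the decision rule unchanged.

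**Conclusion.** The concern holds and must be fixed, because it governs a primary conclusion. The flaw in the inference does not depend on any assumed number: no margin is defined, and absence of significance is taken as proof. The practical size does depend on the unknown SD of study-minus-own differences. At n = 20 and one-sided 0.05, the chance of passing a true 1 dB deficit runs from 0.02% to 30% for SDs of 0.822 to 2.0 dB, and for a 0.5 dB deficit from 16% to 71%. The Objective 8 figures rest on assumed benchmarks. The calculations assume roughly normal paired differences, as 7.1 does.

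**What to change.** Replace the Objective 2 hypotheses in 4.2.1 and the matching sentence in 7.2 with:

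> H0: mean of SRT(study HA) − SRT(own HA) ≥ M. H1: this mean < M. Non-inferiority is concluded only if the upper limit of the two-sided 95% confidence interval for the mean paired difference is below M. A non-significant difference is not interpreted as non-inferiority.

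The sponsor must state and justify M before the data are seen and reconcile it with the definition in 4.1. The 1 dB figure is an obvious candidate, but using a clinically meaningful improvement as an acceptable loss is a new decision. One-sided 0.025 fits the way 7.1 was calculated. One-sided 0.05 would also cure the missing-margin problem if chosen explicitly.

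For Objectives 4, 6, 7 and 8, delete the clauses that convert a non-significant result into non-inferiority, and report the difference or proportion with its 95% confidence interval, unless a margin is stated for that endpoint.

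The cost is wording plus one justified margin. Whether 20 subjects suffice for Objective 2 depends on M and the SD. Power with a true difference of zero and one-sided 0.025:

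| M (dB) | n | SD 0.822 | SD 1.3 | SD 2.0 |
|---|---|---|---|---|
| 1.0 | 20 | >0.99 | 0.90 | 0.56 |
| 1.0 | 16 | 0.99 | 0.82 | 0.46 |
| 0.5 | 20 | 0.73 | 0.37 | 0.19 |

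At one-sided 0.05, M = 1 dB and n = 20, power is 0.95 (SD 1.3) or 0.70 (SD 2.0). For 80% power at one-sided 0.025, n must be 16 (M = 1, SD 1.3), 34 (M = 1, SD 2.0) or 56 (M = 0.5, SD 1.3). The downside is that the claim can now fail because the interval is too wide. For the secondary objectives no margin or SD is documented, so their power is unknown and the change is a correction of wording.
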